C-SSRS			X	C-SSRS should be completed before any other tests, procedures, or consultations to prevent influencing participant perceptions. The investigator/trained study site personnel will interview the participant and complete the C-SSRS.
Clinical Laboratory Assessi	ments			
Chemistry			X	
Ongoing Participant Review	V			
Concomitant therapy	X			
AEs	X			
Crohn's disease-related surgeries and procedures	X			

Footnotes:

- The visit window should be ±7 days.
- b. Study procedures should be performed on-site when they coincide with a q16w visit and at Week 248 (eg, urine pregnancy test, TB evaluation/other infection assessment, injection-site evaluation, concomitant therapy, AEs, and Crohn's disease-related surgeries and procedures).
- c. All participants should have visits q4w via telemedicine (if allowed per local regulation) between on-site visits.

Abbreviations: AE=adverse event; C-SSRS=Columbia-Suicide Severity Rating Scale; q4w=every 4 weeks; q8w=every 8 weeks; q16w=every 16 weeks; SC=subcutaneous; TB=tuberculosis

Table 5: Schedule of Activities: Study Intervention Discontinuation (SID) Visit and the Final Efficacy and Safety (FES) Follow-up Visit

(a) Participants should complete the SID and/or the FES visits, as outlined below

	SIDa	FESb	Notes
Participant terminates study participation at any time during the study	X		Evaluations for SID should be completed prior to participant terminating study participation
Participant discontinues study intervention at or prior to the Week 12 visit	X*	X#	# If the SID visit occurs at or after the Week 8 time point, video ileocolonoscopy and biopsy samples should be done at the SID visit. # If the SID visit occurs prior to the Week 8 time point, video ileocolonoscopy and biopsy samples should be done at the FES follow-up visit instead of the SID visit.
Participant discontinues study intervention after Week 12 and up to the Week 48 visit	X	X	Discontinuation after Week 12 (visit and ileocolonoscopy) and before Week 44: A video ileocolonoscopy (with biopsy samples) is optional to be performed as part of the SID visit. Discontinuation at Week 44 or Week 48: A video ileocolonoscopy (with biopsy samples) is required at the Week 48 visit (or can be performed as part of SID visit).

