10.10. Appendix 10: Study Conduct During a Natural Disaster

GUIDANCE ON STUDY CONDUCT DURING THE COVID-19 PANDEMIC

It is recognized that the COVID-19 pandemic may have an impact on the conduct of this clinical study due to, for example, self-isolation/quarantine by participants and study site personnel; travel restrictions/limited access to public places, including hospitals; study site personnel being reassigned to critical tasks.

In alignment with recent health authority guidance, the sponsor is providing options for study-related participant management in the event of disruption to the conduct of the study. This guidance does not supersede any local or government requirements or the clinical judgement of the investigator to protect the health and well-being of participants and site staff. If, at any time, a participant's safety is considered to be at risk, study intervention will be discontinued, and study follow-up will be conducted.

Scheduled visits that cannot be conducted in person at the study site will be performed to the extent possible remotely/virtually or delayed until such time that on-site visits can be resumed. At each contact, participants will be interviewed to collect safety data. Key efficacy endpoint assessments should be performed if required and as feasible. Participants will also be questioned regarding general health status to fulfill any physical examination requirement.

Every effort should be made to adhere to protocol-specified assessments for participants on study intervention, including follow up. Modifications to protocol-required assessments may be permitted via COVID-19 Appendix after consultation with the participant, investigator, and the sponsor. Missed assessments/visits will be captured in the clinical trial management system for protocol deviations. Discontinuations of study interventions and withdrawal from the study should be documented with the prefix "COVID-19-related" in the eCRF.

The sponsor will continue to monitor the conduct and progress of the clinical study, and any changes will be communicated to the sites and to the health authorities according to local guidance. If a participant has tested positive for COVID-19, the investigator should contact the sponsor's responsible medical officer to discuss plans for study intervention and follow-up. Modifications made to the study conduct as a result of the COVID-19 pandemic should be summarized in the clinical study report.

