From Week 12 through Week 48, participants may transiently use (ie, for <4 weeks) increased doses of corticosteroids for reasons other than treatment for Crohn's disease (eg, stress doses of corticosteroids for surgery, asthma, adrenocortical insufficiency).

After Week 48 and through Week 96, concomitant therapies for Crohn's disease including 5-ASAs, corticosteroids, antibiotics, and immunomodulators (ie, AZA, 6-MP, or MTX), and/or total parenteral or enteral nutrition may be administered and changed at the discretion of the investigator.

Participants who discontinue study intervention early should return for a study intervention discontinuation (SID) visit. All randomized participants should complete the FES follow-up visit approximately 12 weeks after the last dose of study intervention.

Randomization and Blinding

Randomization will be used to minimize bias in the assignment of participants to treatment groups, to increase the likelihood that known and unknown participant attributes (e.g., demographic and baseline characteristics) are evenly balanced across treatment groups, and to enhance the validity of statistical comparisons across treatment groups. Blinded treatment will be used to reduce potential bias during data collection and evaluation of clinical endpoints.

Central randomization will be implemented in this study. It is based on a computer-generated randomization schedule prepared before the study by or under the supervision of the sponsor. Allocation to treatment groups will be performed using an interactive web response system (IWRS). The IWRS will assign a unique treatment code, which will dictate the treatment assignment and matching study intervention kit(s) for the participant.

At Week 0, a target of 318 total participants will be randomly assigned in a 1:1:1 ratio to one of the treatment groups using a permuted block randomization. The randomization will be stratified by baseline Crohn's Disease Activity Index (CDAI) score (\leq 300 or >300), baseline Simple Endoscopic Score for Crohn's Disease (SES-CD) score (\leq 12 or >12), and prior BIO-Failure status (Yes or No).

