5.1.1. Visit Windows

Unless otherwise specified, nominal scheduled visits (described in SoA of the protocol) will be used for over time summaries and listings with no visit windows applied. However, the Unscheduled Visit (USV), Study Intervention Discontinuation (SID) and Final Efficacy and Safety (FES) visits will be slotted to scheduled visits according to the following mapping rules except for SES-CD endpoint:

- 1. Assign a visit number to USV, SID or FES visit based on the Study Day as illustrated in Table 2
- 2. If USV, SID or FES visit falls in the window of a scheduled visit and there are not already data for the scheduled visit, assign the scheduled visit number to the USV, SID or FES visit. If there are already data for a same scheduled visit, those data will be used in lieu of the USV, SID or FES visit data.

Week 4	Day 2-42
Week 8	Day 43-70
Week 12	Day 71-98
Week 16	Day 99-126
Week 20	Day 127-154
Week 24	Day 155-182
Week 28	Day 183-210
Week 32	Day 211-238
Week 36	Day 239-266
Week 40	Day 267-294
Week 44	Day 295-322
Week 48	Day 323-350
Week 52	Day 351-378
etc.	
Week 96	Day 659-686

Table 2: SID/FES/Unscheduled Visit Slotting

More frequent measurements are taken for other endpoints compared to endoscopic assessments taken only at Weeks 0, 12, 48, and 96.

For SES-CD endpoint using a wider window: +/- 4 weeks

Week 12: Days 57 to 113

Week 48: Days 309 to 365

Week 96: Days 645 to 701

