A binary response variable (response/nonresponse) where response is defined as achieving endoscopic response (\geq 50% improvement from baseline in SES-CD score) at Week 12 without experiencing any of the ICEs in categories 1 to 3 and 5 as outlined above prior to the Week 12 visit.

Intercurrent events and corresponding strategies:

The same ICEs and corresponding strategies that are specified for the co-primary endpoint of clinical remission at Week 12 will be used.

Population-level summary:

Difference in proportions of responders (according to the **Variable** defined above) between the combined guselkumab group and the placebo group.

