6.2. Appendix 2 Prohibited Changes in CD Medications (Intercurrent Event 2)

(1) **Prohibited medications**

Initiation of the following prohibited medications after Week 0

- a. Immunomodulatory agents other than AZA, 6-MP, or MTX (including, but not limited to, 6-thioguanine, cyclosporine, mycophenolate mofetil, tacrolimus, and sirolimus).
- Immunomodulatory biologic agents (including, but not limited to, TNFα antagonists, natalizumab, ustekinumab, rituximab, vedolizumab).
- c. Experimental Crohn's disease medications (including, but not limited to, upadacitinib, filgotinib, ozanimod, etrolizumab, brazikumab, mirikizumab, risankizumab, and andecaliximab).
- d. Thalidomide or related agents.

(2) Corticosteroids

The occurrence of the following changes in corticosteroid usage during induction treatment (ie, before week 12), OR, between week 36 and week 48, including changes initiated before week 36 and continued after week 36, unless otherwise specified.

- a. Initiation of oral corticosteroids (including budesonide and beclomethasone dipropionate), parenteral, or rectal corticosteroids due to worsening Crohn's disease.
- b. Increase in the dose of oral corticosteroids (including budesonide and beclomethasone dipropionate), as specified below, above the baseline dose due to worsening Crohn's disease.
 - i. Oral corticosteroids > 5 mg/day (prednisone equivalent)
 - ii. Oral budesonide > 3 mg/day
 - iii. Oral beclomethasone dipropionate > 5 mg/day
- c. Initiation of oral corticosteroids (including budesonide and beclomethasone dipropionate) due to reasons other than worsening Crohn's disease for more than 7 days during induction treatment, OR, for more than 28 days during maintenance treatment.
- d. Increase in the dose of oral corticosteroids (including budesonide and beclomethasone dipropionate), as specified below, above the baseline dose due to reasons other than worsening Crohn's disease for more than 7 days during induction treatment, OR, for more than 28 days during maintenance treatment.
 - i. Oral corticosteroids > 5 mg/day (prednisone equivalent)
 - ii. Oral budesonide > 3 mg/day
 - iii. Oral beclomethasone dipropionate > 5 mg/day

(3) Immunomodulator agents

- a. Initiation of oral 6-MP/AZA due to worsening Crohn's disease.
- b. Initiation of oral, subcutaneous, or intramuscular MTX due to worsening Crohn's disease.
- c. Increase in the dose of oral 6-MP/AZA above the baseline dose due to worsening Crohn's disease.

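### Endoscopies up to 28 days after the nominal Week 12 or Week 48 day can be used, but intercurrent events count only up to the visit, so a rare late scope after surgery or new Crohn's medication can be scored as a response

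*SAP*

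**What the plan says.** **Window.** SAP 5.1.1 states that "nominal scheduled visits (described in SoA of the protocol) will be used for over time summaries and listings with no visit windows applied", and then slots unscheduled, study intervention discontinuation (SID) and final follow-up (FES) data to scheduled visits by two mapping rules. SES-CD is excepted from those rules and has its own line: "For SES-CD endpoint using a wider window: +/- 4 weeks". For the co-primary time point this is "Week 12: Days 57 to 113"; for Week 48 it is Days 309 to 365.

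**ICE cut-off.** In SAP 5.3.2.1, endoscopic response at Week 12 requires at least 50% SES-CD improvement "without experiencing any of the ICEs in categories 1 to 3 and 5 as outlined above prior to the Week 12 visit". SAP 5.5.3 applies the estimand approach of 5.4.2.1 to endoscopic response at Week 48. That estimand also stops at the visit and adds ICE 6 (meeting rescue criteria), handled as composite.

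**Medication changes.** SAP Appendix 2, item (2), counts steroid changes before Week 12, or "between week 36 and week 48, including changes initiated before week 36 and continued after week 36". After Week 48, Crohn's therapies "may be administered and changed at the discretion of the investigator" (SAP 1.2; likewise Protocol 6.8.1).

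**When the scope is due.** Protocol Tables 2 and 3 require the ileocolonoscopy either at the designated visit or at least 10 days ahead of it. Table 5 provides for scopes at SID and, for those who stop before Week 8, at FES.

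**The concern.** The composite strategy declares that surgery, a prohibited medication change or stopping treatment is a failed outcome. That works only if the period over which such events are counted reaches the measurement being scored. Here the measurement may be up to four weeks later than the nominal day, while the count of events stops at the visit. Anything that happens in between is ignored, and the later SES-CD value decides the result.

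Two endpoints in the multiplicity-controlled sequence depend on this rule: the co-primary endoscopic response at Week 12, and endoscopic response at Week 48 for each dose group.

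**Working it through.** **1. Days.** Day 1 is the first dose (SAP 5.1), so Week w falls on Day 7w + 1.

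- Week 12: 7 × 12 + 1 = 85; 113 − 85 = 28 days.
- Week 48: 7 × 48 + 1 = 337; 365 − 337 = 28 days.
- With the protocol visit windows (±4 days to Week 12, ±7 after), and taking randomisation and first dose as the same day, the actual visits fall on Days 81–89 and 330–344. The longest time from visit to last usable scope is then 113 − 81 = 32 days at Week 12 and 365 − 330 = 35 days at Week 48.

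**2. Is an event between the visit and a late scope counted?**

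| Event in the gap | Week 12 | Week 48 |
|---|---|---|
| Crohn's surgery | No (after visit) | No (after visit) |
| Prohibited agent, immunomodulator, 5-ASA or antibiotic | No (after visit) | No (after visit) |
| Steroid start or increase | No (after visit, and the Appendix 2 period has closed) | No (same two reasons) |
| Rescue | Not an ICE at Week 12, but see step 3 | Yes, through ICE 6 |

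Surgery can act on the score directly. The main SES-CD approach (SAP 5.3.1) sums only the segments scored at that examination, so a resected segment can drop out and lower the total.

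**3. Rescue at Week 12.** The first rescue dose is at Week 16: 7 × 16 + 1 = Day 113, or Day 106 at the earliest. The SES-CD window ends on Day 113, so a slotted scope can follow rescue by at most 7 days.

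**4. Planned analyses.** Supplementary Estimand 4 (SAP 5.3.2.2) keeps the same visit cut-off. The tipping-point and multiple-imputation analyses (5.3.5) vary only the missing-data assumptions. The segment-matched analysis (5.3.6.2) carries a missing segment's baseline score forward, so it would soften the resection effect at Week 12, but it does not move the ICE cut-off.

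**5. Size.** First the plan's own figure: 13% versus 30%, n = 106 and 212, two-sided 0.05. The pooled-variance normal approximation is

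power = Φ[(d − 1.96 × se0) / se1]

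- pooled rate = (106 × 0.13 + 212 × 0.30) / 318 = 0.2433
- se0 = √[0.2433 × 0.7567 × (1/106 + 1/212)] = 0.05104
- se1 = √[0.13 × 0.87/106 + 0.30 × 0.70/212] = 0.04536
- (0.17 − 0.10004) / 0.04536 = 1.542, so power is 93.8%; the plan states 94%.

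The documents do not say how many scopes follow the visit. Assumed ranges: 2–10% of participants scoped late, 5–20% of those with an event in the gap, and 30–50% of those scored as responders.

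- Low: 0.02 × 0.05 × 0.30 = 0.0003, i.e. 0.06 of 212 or 0.03 of 106.
- High: 0.10 × 0.20 × 0.50 = 0.01, i.e. 2.1 of 212 or 1.1 of 106.

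The high end is one percentage point. The same formula then gives:

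- Credit to placebo only (14% versus 30%): power 90.2%.
- Credit to both arms (14% versus 31%): power 93.1%.
- Credit to guselkumab only, with no true effect (13% versus 14%): upper-tail error 4.2% instead of 2.5%.

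The one-sided cases are extremes, because nothing in the plan confines late scopes to one arm.

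**The case against.** The strongest reply is that the protocol already orders the two events. With endoscopy due before or at the visit, a later scope is a deviation or an unscheduled, SID or FES examination. Early discontinuers scoped at FES are already non-responders through ICE 3 or 5, unless they stopped under ICE 4. A prohibited agent forces discontinuation, and Table 5 places the SID visit at that time, so its scope would follow a new biologic almost at once. FES after a Week 12 dose falls near Day 85 + 84 = 169, outside the window. All of this stands, and it is why the point is small. It does not cover surgery, or the conventional Crohn's medicines, which do not force discontinuation.

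The visit in the responder definition could also be read as the date of the slotted assessment. The SAP does not say so, and the renumbering rule that would support this reading excepts SES-CD. Nor would it close the steroid gap, since the Appendix 2 periods end at Weeks 12 and 48 regardless.

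A reader might infer three stronger claims, none of which the documents support:

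- **Rescue is credited to placebo.** At Week 48 rescued participants are non-responders through ICE 6. At Week 12 the overlap is at most 7 days after one dose.
- **Scopes labelled with the scheduled visit have no time limit.** SAP 5.1.1 applies its no-window rule unless otherwise specified, and the SES-CD line may be that specification. The text is unclear rather than wrong.
- **The protocol foresees scopes trailing visits.** Table 5 names visit and scope separately ("Discontinuation after Week 12 (visit and ileocolonoscopy) and before Week 44") but expects both to be done by then. Protocol Appendix 10 speaks of visits being "delayed until such time that on-site visits can be resumed", which moves the cut-off along with the visit. Only a remotely held visit would separate the two.

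**Conclusion.** The mismatch is in the text. SES-CD is accepted up to 28 days past the nominal day, events are counted to the visit, and no planned analysis shifts that cut-off. It can misclassify a responder on a co-primary endpoint and on a multiplicity-controlled Week 48 endpoint. The gap is widest at Week 48, because Crohn's therapies may then change without restriction.

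It is a minor point. It concerns exceptional scopes only, and the whole 28 days should not be read as time at risk. The estimate of at most about two guselkumab participants and one placebo participant at Week 12 rests entirely on the assumed ranges. Credit to placebo would cost power and credit to guselkumab would raise the false-positive risk, so the direction is not fixed.

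**What to change.** For endoscopic response at Week 12 and Week 48, and the other SES-CD responder endpoints:

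1. In SAP 5.3.2.1 and 5.5.3, count composite ICEs up to the later of the visit date and the date of the endoscopy used. Keeping the later date preserves the present treatment of an event after an early scope but before the visit.
2. In Appendix 2, item (2), run the steroid periods to that same date for these endpoints.
3. In SAP 5.1.1, state which endoscopy is used when more than one falls in the window, since the precedence rule sits in the list that excepts SES-CD. State also whether the SES-CD window applies to scopes labelled with the scheduled visit.

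No separate rescue rule at Week 12 is needed, and the point does not call for discarding scheduled-visit scopes that fall outside the window.

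The cost is a few sentences and some programming from dates already collected. Design rates and sample size do not change, so planned power stays at 93.8%. The downside is that a few more participants may become non-responders.

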5.2. Participant Disposition

The number of participants in each analysis set, including the Randomized Analysis Set, will be summarized by treatment group, combined guselkumab treatment group and overall. In addition, the distribution of participants by region, country and site ID will be presented.

The number and frequency of participants in the following disposition categories will be summarized by treatment group, combined guselkumab group, and overall based on the FAS.

Note that "major disruption-related discontinuations" and "major disruption-related terminations" are study intervention discontinuations or study terminations that were due to unforeseen major disruptions such as a regional crisis.

- Participants who received study intervention by visit
- Participants discontinuing **study intervention** prior to Week 12 and reasons for discontinuation, including those due to COVID-19 related events and other major disruption-related discontinuations.
- Participants discontinuing **study intervention** prior to Week 24 and reasons for discontinuation, including those due to COVID-19 related events and other major disruption-related discontinuations.
- Participants discontinuing **study intervention** prior to Week 48 and reasons for discontinuation, including those due to COVID-19 related events and other major disruption-related discontinuations.

- Participants discontinuing **study intervention** prior to Week 92 and reasons for discontinuation, including those due to COVID-19 related events and other major disruption-related discontinuations.
- Participants who terminated **study participation** prior to Week 12 and reasons for termination, including those due to COVID-19 related events and other major disruption-related terminations.
- Participants who terminated **study participation** prior to Week 24 and reasons for termination, including those due to COVID-19 related events and other major disruption-related terminations.
- Participants who terminated **study participation** prior to Week 48 and reasons for termination, including those due to COVID-19 related events and other major disruption-related terminations.
- Participants who terminated **study participation** prior to the end of study and reasons for termination, including those due to COVID-19 related events and other major disruption-related terminations.
- All participants who met the rescue criteria.

Listings of participants will be provided for the following categories:

- Participants who discontinued study intervention
- Participants who terminated study participation
- Participants who were randomized yet did not receive study intervention
- Participants who were unblinded prior to study unblinding

Study Assessment Compliance will be summarized and listed by randomized treatment group. This will include the number of participants who missed at least one scheduled CDAI assessment, at least one scheduled endoscopy assessment, intercurrent events, or at least one study intervention administration due to any reason, including COVID-19 related events and other major disruptions.

5.3. Co-Primary Endpoints Analysis

5.3.1. Definition of Endpoints

The co-primary endpoints are:

- Clinical remission at Week 12
- Endoscopic response at Week 12

Clinical remission is defined as a CDAI score <150.

Endoscopic response is defined as \geq 50% improvement from baseline in Simple Endoscopic Score for Crohn's Disease [SES-CD].

CDAI score

The CDAI is a validated multi-item measure of severity of illness derived as a weighted sum of 8 different Crohn's disease-related variables. These 8 variables are:

- extra-intestinal manifestations
- abdominal mass
- weight
- hematocrit
- use of antidiarrheal drug(s) and/or opiate
- total number of liquid or very soft stools
- abdominal pain/cramps
- general well-being.

Calculation of the CDAI score:

Two approaches to calculating the CDAI score are provided below. The main approach will be used for the analysis of all endpoints that include the CDAI; of particular note is that this main approach is used for the co-primary and secondary endpoints that involve the CDAI. Additional analyses of co-primary and secondary endpoints that involve the CDAI will also be provided using the alternative approach.

Main approach

The last 3 components of the CDAI score listed above are scored over 7 days by the participant on a diary card. For the total number of liquid or very soft stools, abdominal pain/cramps, and general well-being, if only 5 days or 6 days of data are available for the calculation, the weights of 7/5 and 7/6, respectively, will be used for the calculation; if the values are recorded for less than 5 days, the component will not be calculated.

The CDAI score calculation algorithm is presented in Section 10.8 Appendix 8 of the study protocol. At each timepoint, the CDAI score will only be calculated if \geq 4 of the 8 components are available. If the CDAI score cannot be calculated (ie, <4 components available), the CDAI score will be considered missing. When at least 4 of the 8 components are available, any missing components will be imputed by carrying forward the last non-missing value for that component.

Alternative approach

For components scored over 7 days (i.e., total number of liquid or very soft stools, abdominal pain/cramps, general well-being), a participant's value for that component will be considered missing if the participant recorded < 4 measurements for that week. If the participant recorded measurements on only 4, 5 or 6 days, the sum of the non-missing daily values will be multiplied, respectively, by a factor of 7/4, 7/5 or 7/6 to obtain a score representative of all 7 days.

At each timepoint, the CDAI score will only be calculated if ≥ 5 of the 8 components are available AND none of the components of the diary data (ie, total number of liquid or very soft stools,

abdominal pain/cramps, and general well-being) are missing. In other words, CDAI will be calculated only if ALL the following conditions are met:

- (1) All 3 components of the diary data are available for at least 4 of 7 days.
- (2) At least 2 other components are available.
- (3) If there are any missing components at a visit, the last non-missing values for the missing items may be carried forward as long as it was collected no earlier than the nominal visit 8 weeks prior to the visit. For example, if a component at the Week 24 visit is missing, the last nonmissing value for the missing component may be carried forward as long as it was collected no earlier than the Week 16 visit.

SES-CD score

The Simple Endoscopic Score for Crohn's Disease (SES-CD) is a scoring system developed to provide a granular evaluation of endoscopic disease severity in patients with Crohn's disease. It is constructed based on the evaluation of 4 endoscopic components across 5 predefined ileocolonic segments. The 4 endoscopic components within each segment are the presence/size of ulcers, the proportion of mucosal surface covered by ulcers, the proportion of mucosal surface affected by any other lesions, and the presence/ type of narrowing (also commonly referred to as strictures/ stenosis clinically). Each endoscopic component is scored from 0 to 3 for each segment, and a total score is calculated as a sum of all the component scores across all the segments, as outlined in Table 3. The total SES-CD score ranges from 0 to 56.

Table 3:Sample score sheet and scoring definitions for the Simple Endoscopic Score for Crohn's Disease
(SES-CD)

	Ileum	Right Colon	Transverse Colon	Left Colon	Rectum	Total
1. Presence and size of ulcers (0-3)						15 max
2. Extent of ulcerated surface (0-3)						15 max
3. Extent of affected surface (0-3)						15 max
4. Presence and type of narrowings (0-3)						11 max*
				T 11		SES-CD
				Total 1 -	-2+3+4 =	(56 max)

	Score = 0	Score = 1	Score = 2	Score = 3
Size of ulcers	None	Aphthous ulcers $(\emptyset \ 0.1 - 0.5 \ \text{cm})$	Large ulcers $(\emptyset 0.5 - 2.0 \text{ cm})$	Very large ulcers $(\phi > 2.0 \text{ cm})$
Ulcerated surface	None	<10%	10-30%	>30%
Affected surface	Unaffected segment	<50%	50-75%	>75%
Narrowing	None	Single, can be passed	Multiple, can be passed	Cannot be passed

* The maximum sub-score for narrowing (i.e. stricturing) is 11 points. The presence of a narrowing that cannot be passed can be only observed once.

ø =Diameter.

Calculation of the SES-CD score:

Two approaches to calculating the SES-CD score are provided below. The main approach will be used for the analysis of all endpoints that include the SES-CD; of particular note is that this main

approach will be used for the co-primary endpoint of endoscopic response at Week 12. A supportive analysis of the endpoint of endoscopic response at Week 12 will also be provided using the alternative approach.

Main approach (SES-CD calculated based on all segments available):

The total SES-CD score at a visit will be calculated based on all segments scored at the visit. If the total SES-CD score cannot be calculated (ie, none of the segments are scored) at a visit, the total SES-CD score will be considered missing.

Alternative approach (baseline segments matched approach):

The SES-CD score at baseline is calculated as the sum of all segments scored at baseline. To calculate the SES-CD score at a post-baseline visit, the sum of the segments that were present at baseline will be used. For segments that were present at baseline but missing post-baseline, the baseline score for the missing segment(s) will be carried forward, unless all segments that were present at baseline are missing at post-baseline, in which case the post-baseline SES-CD score will be assigned as missing. In the event that a segment is missing at baseline but non-missing post-baseline, the non-missing post-baseline score is not used in the calculation of SES-CD for all post-baseline evaluations.

